Meta-analyses of 24 published studies reveal that CT and MRI perform equally poorly in the detection of lymph node metastases from prostate cancer [31]. Results of pooled sensitivity and specificity are 42% and 82%, respectively, for CT and 39% and 82%, respectively, for MRI. Thus, the reliance on either CT or MRI may misrepresent the patient's true status regarding nodal metastases, and misdirect the therapeutic strategies offered to the patient [31]. Radionuclide bone scans are commonly used for monitoring bone metastases. However, as bone scans detect tissue remodeling, as opposed to tumor burden, false positives can be caused by inflammation, previous bone injuries, and arthritis, especially in older men [32].

One of the most challenging aspects of clinically managing prostate cancer is the development of suspected or known disease recurrence after initial definitive therapy. Rising PSA after initial definitive therapy is known as biochemical recurrence (BCR) of prostate cancer and may occur in 20-30% of prostate cancer patients before a more definitive diagnosis of metastatic disease can be established by conventional imaging modalities [33-36].

Therefore, new agents that will detect and localize the primary tumor, as well as small metastatic lesions, with high sensitivity and specificity are essential to more accurately diagnose and stage the disease and monitor therapy.

This particular study aims to focus on the detection of metastatic disease or local recurrence early on in prostate cancer patients with biochemical recurrence. This group of prostate cancer patients after definitive local therapy currently have limited imaging options in the United States. The current standard-of-care imaging tests detect local recurrence or metastatic lesions long after when the serum PSA levels become detectable. Also, these imaging tools are not sensitive or

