 - If patients with solitary visceral metastasis show a decrease of PSA by greater than 50% after targeted treatment (i.e. external beam radiation) and lesions do not change in size (less than 30% decrease or 20% increase in largest diameter).

b. False positive:

- If on follow-up imaging within 3-12 months, sites of initial PET positive lesions seen on CT or MRI scan decrease by more than 30% without systemic therapy or focal therapy at this site.
- If ¹⁸F-DCFPyL PET positive lesions do not meet the criteria for above false positive or true positive findings.
- 3. ¹⁸F-DCFPyL PET positive bone lesions will be considered:
 - a. True positive:
 - If there was a corresponding positive sclerotic lesion on the CT portion of the ¹⁸F-DCFPyL PET in the same location as the focal uptake.
 - If there is focal uptake seen on the baseline bone scan performed within one month of ¹⁸F-DCFPyL PET.
 - If there is a lesion noted on the initial MRI imaging scan performed within one month of ¹⁸F-DCFPyL PET.
 - If within 12 months follow-up CT scan demonstrates development of sclerosis.
 - If within 12 months follow-up MRI scan demonstrates a new bone lesion.
 - If within 12 months follow-up bone scan demonstrates new focal uptake.

b. False positive:

- If ¹⁸F-DCFPyL PET positive bone lesions do not meet the criteria for true positive findings.
- 4. ¹⁸F-DCFPyL PET positive prostate bed and prostate lesions will be considered:
 - a. True positive:
 - If on follow-up imaging within 12 months, lesions seen on CT or MRI scan decrease by 30% (for patients undergoing systemic treatment of focal therapy at this site) or increase by 20% in largest diameter.

• If patients with prostate bed lesions show a decrease of PSA by greater than 50% after targeted treatment (i.e. external beam radiation) and lesions do not change in size (less than 30% decrease or 20% increase in largest diameter).

b. False positive:

- If on follow-up imaging within 3-12 months, sites of initial ¹⁸F-DCFPyL PET positive lesions seen on CT or **MRI** scan decrease by more than 30% without systemic therapy or focal therapy at this site.
- If ¹⁸F-DCFPyL PET positive lesions do not meet the criteria for above false positive or true positive findings.

Histopathology/Biopsy:

- 1. Localization of lesions for histopathology/biopsy will be classified according to the regions in table (Definition of regions) below.

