- 2. The ¹⁸F-DCFPyL PET positive findings will be targeted to be confirmed by histopathology/biopsy if and whenever clinically feasible.
- 3. Histopathological procedures, biopsies and follow-up imaging will be performed as clinically indicated and as per the standard of care/institutional protocol. The following elective procedures may guide the investigator:
 - A. Positive HP/Biopsy: Confirmed sites of metastatic or tumor involvement by histopathology/biopsy will be discussed with the responsible physician/surgeon.
 - B. Negative Biopsy: Patients with suspected tumor recurrence on the PET with negative histopathology/biopsy will be handled as outlined below:

1. Lymph nodes:

- For patients undergoing nodal dissection: Patients will be rescanned with dedicated CT or MRI scan, if clinically feasible, to determine if the suspicious ¹⁸F-DCFPvL PET positive node was removed.
 - o If PET positive lymph node is still present, a repeat biopsy can be pursued if clinically feasible and applicable, or follow-up using imaging as described above will be performed.
 - o If the corresponding node was removed, then this will be considered a False Positive.
- For patients undergoing needle biopsy: Images of the procedure will be reviewed to determine if the correct node was biopsied.
 - o If the correct node was biopsied, then a negative biopsy will be considered a False Positive.
 - o If the incorrect node was biopsied, then follow-up imaging as described above will be performed if clinically feasible.

- 11. Bone lesions: Given the high rate of false negative biopsies for osseous metastases in patients with prostate cancer, patients with negative bone biopsies of PET positive lesions will be further evaluated:
 - If pathology demonstrates alternative diagnoses that is known to be PET positive (e.g. Renal Cell Carcinoma metastases, Paget's disease), then this will be considered a False Positive.
 - If pathology is indeterminate, then follow-up imaging as described above will be performed to determine if the lesion is a True Positive or False Positive.
- Additionally, a repeat ¹⁸F-DCFPyL PET may also be obtained as per treating physician discretion in addition to repeat conventional imaging (CT and/or MRI) in cases of negative biopsy to determine if the biopsy was true negative or false negative.
- C. Although not routinely performed during standard practice, immunohistochemical or specimens (primary and lymph node metastases) may be performed, although not required.

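### A bone-scan focus or MRI lesion reported as benign can still make an unbiopsied PET-positive bone lesion a true positive

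*Combined protocol and SAP*

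**What the plan says.** Section 3.5.1 lists the ways in which a PET-positive bone lesion is validated as a true positive. They are alternatives, so one is enough. In protocol order:

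1. A sclerotic lesion on the CT part of the PET, "in the same location as the focal uptake".
2. "If there is focal uptake seen on the baseline bone scan performed within one month of" the study PET.
3. "If there is a lesion noted on the initial MRI imaging scan performed within one month of" the study PET.
4. "If within 12 months follow-up CT scan demonstrates development of sclerosis".
5. "If within 12 months follow-up MRI scan demonstrates a new bone lesion".
6. "If within 12 months follow-up bone scan demonstrates new focal uptake".

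The only false-positive rule for bone is residual: a lesion that meets none of the six is a false positive.

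Three other places bear on this:

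- Section 1.2 says of bone scans that "false positives can be caused by inflammation, previous bone injuries, and arthritis, especially in older men".
- The biopsy rules in Section 3.5.1 class a bone lesion as a false positive "If pathology demonstrates alternative diagnoses that is known to be PET positive (e.g. Renal Cell Carcinoma metastases, Paget's disease"). Biopsy is sought only where clinically feasible, and indeterminate bone pathology is referred back to imaging follow-up.
- Section 3.10.1 ranks histology above imaging and imaging above PSA. It leaves validation to unblinded local investigators who apply the prespecified criteria.

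**The concern.** Routes 2 and 3 ask only that something is visible on a bone scan or MRI close to the PET. They do not ask what the report says it is. A benign process that takes up both tracers, or that shows on MRI, then confirms itself. The protocol recognises that such processes exist, both in its account of bone scanning and in its Paget's disease example, but it acts on this only when tissue is obtained. The class given to a benign bone focus can therefore turn on whether it happened to be biopsied.

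The true-positive count is the numerator of both endpoints. The bone region is one of the four regions of the secondary endpoint and is affected directly. The primary, per-patient PPV is affected where bone is the patient's only PET-positive site, or the only site validated as true positive.

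A smaller matter is that routes 2 to 6 do not state that the correlate must be at the PET focus, although route 1 does.

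**Working it through.** **Rules side by side.** Take one benign focus, for example Paget's disease, that is PET-positive in bone.

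- Biopsied, with the alternative diagnosis shown: false positive under the biopsy rules.
- No diagnostic histology, focal uptake on a baseline bone scan that the report attributes to Paget's disease: route 2 is met, so true positive.
- No diagnostic histology, a lesion on the initial MRI reported as benign: route 3 is met, so true positive.
- No diagnostic histology and none of the six routes met: false positive under the residual rule.

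The lesion is the same and only the available evidence differs. In the second and third cases the report already names a benign cause, and the written rule does not let it count.

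**Which routes are most exposed.** Routes 1 and 4 require sclerosis, and routes 4 to 6 require change during follow-up. A long-standing benign finding already visible at baseline does not meet routes 5 and 6. Routes 2 and 3 need neither a particular appearance nor change, so the gap is mainly there. No route excludes a benign explanation in words.

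**The plan's own figures.** Section 3.10.2 expects 0.85 × 300 = 255 PET-positive patients. The exact 95% interval for 204/255 (80%) is 74.6% to 84.7%, which matches the tabulated 75% to 85%, a half-width of about 5 points. These intervals cover sampling error only. Misclassification is not in them and does not shrink with sample size.

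**Scale, by assumption only.** The inflation of per-patient PPV from this one error is b × f × m, where

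- b = share of PET-positive patients whose only PET finding is in bone,
- f = share of those foci that are benign,
- m = share of those benign foci that meet a true-positive route.

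The documents give none of the three. Assumed ranges are b = 5–20%, f = 20–60% and m = 25–100%.

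- Low: 0.05 × 0.20 × 0.25 = 0.0025, or 0.25 points; × 255 = 0.6 patients.
- Middle: 0.10 × 0.40 × 0.50 = 0.02, or 2 points; × 255 = 5.1 patients. With an assumed non-bone PPV of 85%, the correct PPV is 0.90 × 0.85 + 0.10 × 0.60 = 82.5%, and the observed PPV would be 84.5%.
- High: 0.20 × 0.60 × 1.00 = 0.12, or 12 points; × 255 = 30.6 patients.

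Within those bone foci the shift is f × m, which only restates the assumptions. If routine care supplies no baseline bone scan or MRI, routes 2 and 3 contribute nothing to m.

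**The case against.** Several points on the other side are sound.

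- *Same lesion implied.* The six routes sit under a lead-in about the PET-positive bone lesion being classified, and Section 3.10.1 describes the exercise as validating lesions. A reader might infer that a new vertebral lesion on follow-up MRI confirms an unrelated rib focus. That reading is strained. The missing site phrase is more likely a drafting gap than a decision to accept unrelated lesions.
- *Filters upstream.* A scan is positive only if a lesion suggests recurrence, and scans are read twice by readers with more than five years of PET experience. Some benign foci would never enter the count.
- *Histology takes precedence.* Where diagnostic tissue exists it overrides imaging, so the gap concerns only lesions without it.
- *Limited exposure.* Appendix A marks conventional imaging only in long-term follow-up. Routes 2 and 3 operate only where routine care supplied a bone scan or MRI within a month of the PET.
- *Opposite errors.* Every unmatched bone lesion is a false positive, and bone has no route through PSA or treatment response, unlike nodes, viscera and prostate bed. A real metastasis with no correlate would be counted as false positive.

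These points limit how often the error occurs and rule out a claim about net direction. They do not remove it. Under any reading of the site question, routes 2 and 3 still accept a correlate reported as benign. An investigator might reject such a correlate on clinical judgement, but the prespecified criteria do not ask for that, and two investigators could classify the same lesion differently.

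**Conclusion.** The concern stands in a limited form. A PET-positive bone lesion without diagnostic histology can be a true positive on the strength of a baseline bone-scan focus or an initial MRI lesion that is itself attributed to a benign cause. That conflicts with the protocol's own account of bone-scan false positives and with its treatment of biopsied Paget's disease. The missing site match in routes 2 to 6 is a clarification.

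This particular error can only raise the bone-region PPV, and the per-patient PPV where bone is the only positive or only validated site. The latter assumes that one validated site makes a patient a true positive.

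A reader might go further and infer that the reported PPV will be biased upward overall, or by a stated number of points. The documents support neither: they give no bone-only share, benign share or availability of baseline imaging, and the residual rule can work in the opposite direction. The 0.25 to 12 point range shows only that the effect could be negligible or could exceed the planned half-width of about 5 points.

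**What to change.** Amend the bone true-positive rules in Section 3.5.1:

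- In routes 2 to 6, add: *at the site of the PET focus*.
- In the bone true-positive rules, above all routes 2 and 3, add: *and not attributed in the report to a benign cause (e.g. degenerative change, fracture, Paget's disease)*.

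No new false-positive rule is needed. A lesion whose only correlate is attributed to a benign cause, with no other qualifying evidence, falls under the existing residual rule.

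The exclusion should cover only correlates reported as benign. Requiring each correlate to be reported as suspicious for metastasis would push equivocal reports into the false-positive class and add an error in the other direction.

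The cost is wording. The reports already exist, and no procedure or patient is added. Observed bone PPV may be somewhat lower, and classification will depend on how local reports are worded.

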3.10 STATISTICAL METHODS PLANNED IN THE PROTOCOL AND DETERMINATION OF SAMPLE SIZE

3.10.1 Study Design

This is a single arm phase II clinical trial to evaluate the positive predictive value (PPV) of ¹⁸F-DCFPyL PET imaging in men diagnosed with prostate cancer with increasing prostate-specific antigen (PSA) levels. PPV is the number of true positives (TP) divided by number of patients who are tested positive (i.e., TP + FP) based on the PET imaging. The determination of TP and positive testing is detailed in Section 3.5.1. Secondary endpoints are PPV of ¹⁸F-DCFPyL PET (per-region). All patients who are diagnosed with prostate cancer with increasing PSA levels and who have received PET scans will be evaluable for the analysis.

All patients will be followed up for histopathologic analysis, conventional imaging (CT, MRI and/or bone scan) and/or serum PSA after focal salvage therapy acquired during clinical routine. Combination of (in descending priority) histopathologic analysis, imaging, and PSA follow-up after local/focal therapy will used for lesion validation. Validation will be performed by the unblinded local investigators after reviewing images and reports, following prespecified criteria of the study protocol. In patients with follow-up, positive ¹⁸F-DCFPyL PET findings will be validated as true or false-positive results. Region negative on ¹⁸F-DCFPyL PET, but with subsequently confirmed prostate cancer by histopathologic analysis, will be considered false-negative results. True negative will not be defined. (please see section 3.5.1. for details).

3.10.2 Sample Size

A total of 300 evaluable participants will be enrolled into this study. We expect approximately 85% of them, i.e., 255 patients, will have positive test results. Based on these 255 patients, the exact 95% confidence interval (CI) for PPV has a width ofless than 12%. The following table shows the exact 95% CI corresponding to different observed PPV values.

Observed PPV	95% CI of true underlying PPV
80%	(75%, 85%)
84%	(79%, 88%)
88%	(84%, 92%)
92%	(88%, 95%)
96%	(93%, 98%)
100%	(99%, 100%)

As an example, from this table, an observed 80% PPV value indicates that we can be 95% confident that the true underlying PPV lies in the interval (75%, 85%). If the observed PPV is 88%, then we can be 95% confident that the true underlying PPV lies in the interval (84%, 92%).

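### Absent positive histopathology, the bone criteria in 3.5.1 have no PSA or treatment-response route, so some treated or progressing bone lesions are scored false positive, in conflict with 3.10.1

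*Combined protocol and SAP*

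**What the plan says.** Section 3.5.1 sets true- and false-positive rules by lesion type. For bone there are six true-positive routes.

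- Three use baseline findings: a "positive sclerotic lesion on the CT portion of the" PET at the site of uptake; "If there is focal uptake seen on the baseline bone scan performed within one month of" the PET; and "If there is a lesion noted on the initial MRI imaging scan performed within one month of" the PET.
- Three use follow-up: "If within 12 months follow-up CT scan demonstrates development of sclerosis"; a new bone lesion on MRI within 12 months; and "If within 12 months follow-up bone scan demonstrates new focal uptake".

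A bone lesion is a false positive if "PET positive bone lesions do not meet the criteria for true positive findings".

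Nodes, visceral lesions and the prostate or prostate bed each have a size-change route, which includes shrinkage under therapy, and a PSA route. The visceral version reads "If patients with solitary visceral metastasis show a decrease of PSA by greater than 50% after targeted treatment", provided that the lesion does not change in size.

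Section 3.10.1 states the reference standard for lesions in general: "Combination of (in descending priority) histopathologic analysis, imaging, and PSA follow-up after local/focal therapy will used for lesion validation". The synopsis describes the same composite standard. Neither excludes bone, and 3.10.1 refers to 3.5.1 for detail. Section 3.5.1 also seeks biopsy confirmation of PET-positive findings where feasible, with a pathway for negative bone biopsies.

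**The concern.** The bone rules recognise a lesion that was already visible on recent imaging or that shows something new afterwards. They do not recognise a response to treatment. They also do not recognise, on MRI or bone scan, the progression of a lesion that an older scan had already shown. A real metastasis with either course can therefore be entered as a false positive.

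Bone is one of the four regions in the secondary endpoint, so its PPV takes these errors directly. The primary per-patient PPV takes them for men who have no other confirmed lesion. Because 3.10.1 admits PSA follow-up and the bone list does not, two validators following the protocol could also score the same treated bone lesion differently.

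**Working it through.** **The plan's own precision.** Section 3.10.2 expects 0.85 × 300 = 255 PET-positive men. Exact (Clopper-Pearson) 95% intervals at n = 255 reproduce its table: 204/255 gives 74.6 to 84.7%, 214/255 gives 78.8 to 88.2%, 225/255 gives 83.6 to 91.9%, 235/255 gives 88.2 to 95.1%, 245/255 gives 92.9 to 98.1%, and 255/255 gives 98.6 to 100%. At 88% the stated interval is 84 to 92%, a half-width of (92 − 84)/2 = 4 points.

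**Routes to true positive in the 3.5.1 imaging and PSA rules, by lesion type.**

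| Lesion type | Baseline finding alone | Size change or response | New or developing finding | PSA fall |
|---|---|---|---|---|
| Nodes | 0 | 1 | 0 | 1 |
| Visceral | 0 | 1 | 0 | 1 |
| Prostate or bed | 0 | 1 | 0 | 1 |
| Bone | 3 | 0 | 3 | 0 |

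All four types have a catch-all false-positive rule.

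**Case 1, treated lesion (constructed example).** A solitary, non-sclerotic, unbiopsied bone focus has no bone-scan or MRI finding within one month of PET. It is irradiated and PSA goes from 3.0 to 0.2 ng/mL, a fall of (3.0 − 0.2)/3.0 = 93%. If no sclerosis or new finding appears within 12 months, all six routes fail and the lesion is a false positive. A solitary nodal region of stable size with the same course is a true positive.

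**Case 2, lesion already visible (constructed example).** A bone scan or MRI six weeks before PET shows the lesion, and the CT part of the PET shows no sclerosis. The one-month limit closes both dated baseline routes. Later growth or increased uptake is not new against the earlier scan, so the MRI and bone-scan follow-up routes fail. Only sclerosis developing on CT can still confirm it. Growth of more than 20% (at least 3 mm) makes a node a true positive.

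**How open these gaps are.** Appendix A schedules conventional imaging only in long-term follow-up, and the eligibility criteria require no baseline bone scan or MRI, so the one-month window depends on routine care. Section 3.5.1 asks for follow-up in the same modality as the initial work-up, so a man staged without CT may have no dedicated follow-up CT. The Appendix A footnote on long-term follow-up allows chart review to end once the patient has responded, possibly before late sclerosis is seen.

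**Size, by assumption.** Let b be the share of PET-positive men whose only finding is in bone, and f the share of their true metastases that meet no route and are not biopsied. The documents give neither; take b = 5 to 20% and f = 10 to 50%. Assume that bone-only men have the same true PPV as the rest. Then

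observed PPV = true PPV × (1 − b × f).

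With a true PPV of 88%:

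- b = 5%, f = 10%: loss 0.88 × 0.05 × 0.10 = 0.4 points
- b = 10%, f = 25%: loss 0.88 × 0.10 × 0.25 = 2.2 points
- b = 10%, f = 50%: loss 0.88 × 0.10 × 0.50 = 4.4 points
- b = 20%, f = 50%: loss 0.88 × 0.20 × 0.50 = 8.8 points

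For the bone region, applying f to all true bone lesions and assuming a true PPV of 90%, observed PPV is 0.90 × (1 − f): 81%, 67.5% and 45% at f = 10%, 25% and 50%.

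**The case against.** A reader might infer that every successfully treated bone metastasis becomes a false positive. The documents do not support that. Histopathology ranks first in the composite standard and is open to every PET-positive finding. A treated lesion is also a true positive if it was sclerotic on the PET's own CT, had a bone-scan or MRI finding within one month, or became sclerotic on CT within 12 months. This part of the objection stands and limits the point to the lesions in the two cases. Biopsy does not close the gap: it depends on feasibility, 3.5.1 itself notes frequent false-negative bone biopsies, and indeterminate pathology goes back to follow-up imaging.

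A reader might also infer that bone PPV is biased downward relative to the other regions. That is not established. Bone has three baseline-only routes that the other types lack, and section 1.2 says that bone scans can be falsely positive from inflammation, old injury and arthritis. Those routes could raise bone PPV.

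The figure of 64% of men with changed intended management, from the phase 3 study described in section 1.1, does not size the problem. It covers intended management for disease at any site, 21.4% of the changes followed negative scans, and the commonest change (58 of 131) was from salvage local to systemic therapy.

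Finally, one can argue that 3.5.1 governs because 3.10.1 defers to it. Then PSA is simply unavailable for bone, but 3.10.1 and the synopsis do not say so. The texts need reconciling on either reading.

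**Conclusion.** The point holds for a defined set of lesions: PET-positive in bone, without positive histopathology, not sclerotic on the PET's CT, with no bone-scan or MRI finding within one month, and with no later sclerosis or new finding. Among these, a solitary lesion with a PSA fall of more than 50% after targeted treatment, and a lesion known from an older scan that progresses, are scored false positive. The evidence in the first case is accepted at the other three sites. In the second, comparable evidence (growth) is accepted there.

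For these lesions the error is towards a lower PPV. Its size cannot be derived from the documents. Under b = 5 to 20%, f = 10 to 50% and a true PPV of 88%, the per-patient loss is about 0.4 to 9 points against a half-width of 4. The upper end combines two assumed maxima. The per-patient figure also assumes that one confirmed lesion makes a man a true positive, a rule that the documents do not spell out. The conflict between 3.5.1 and 3.10.1 needs no assumption.

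**What to change.** Reconcile the bone criteria in 3.5.1 with 3.10.1 and the synopsis by two changes to the true-positive list.

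1. Add a PSA criterion for a solitary bone lesion after targeted treatment, parallel to the other sites. Leave out the diameter condition where the lesion has no measurable correlate, since it could not then be applied.
2. In the follow-up MRI and bone-scan criteria, replace 'new' with 'new or increased', and state that the finding must be at the PET-positive site.

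Do not add an indeterminate category for bone alone. It would remove lesions from the PPV denominator, give bone an exemption that no other site has, and sit badly with 3.10.1, which treats all scanned men as evaluable. At most, report a sensitivity analysis of bone-region and per-patient PPV that excludes treated, unconfirmed bone lesions.

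The cost is scoring text. PSA, treatment and imaging are already reviewed at 3, 6, 9 and 12 months, and no visit or scan is added. The downside is that a PSA response is weaker evidence than imaging, which the plan already accepts for the other three lesion types.

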- 3. Bone lesions will be considered positive if the uptake is focal and greater than normal marrow uptake.
- 4. Prostate bed and prostate lesions will be considered positive if uptake is focal and greater than background activity of the prostate.

Follow-up imaging:

A chart review will be performed at 3, 6, 9 and 12 months with a plan to communicate with the referring oncologist team regarding the plan for follow-up imaging with a CT, MRI and/or bone scan. If a follow-up imaging is not obtained by 12 months, then imaging will be requested. Interpretation of follow-up imaging will be performed by local read. The follow-up conventional imaging should be the same modality/modalities as the initial staging work-up to allow for reproducible and accurate comparisons.

PET positive findings will be validated as true or false positive as outlined in more detail below. False negative ¹⁸F-DCFPyL PET findings cannot be determined as this would require biopsies of all PET negative lesions that are present on conventional imaging.

¹⁸F-DCFPyL PET validation will be based on follow-up imaging:

- 1. Lymph nodes will be assessed by change in size. PET positive lymph nodes will be considered:
 - a. True positive:
 - If on follow-up imaging within 3-12 months, lymph nodes seen on CT or MRI scan decrease by more than 30% (for patients undergoing systemic treatment of focal therapy at this site) or increase by more than 20% in short axis diameter (with a minimum of 3 mm in change in size).
 - If patients with solitary lymph node regions show a decrease of PSA by greater than 50% after targeted treatment (i.e. external beam radiation) and the lymph nodes do not change in size (less than 30% decrease or less than 20% increase in short axis diameter).

b. False positive:

• If on follow-up imaging within 3-12 months, sites of initial ¹⁸F-DCFPyL PET positive lymph node lesions seen on CT or MRI scan decrease by more than 30% without systemic therapy or focal therapy at this site.

- If PET positive lymph node lesions do not meet the criteria for above false positive or true positive findings.
- 2. Visceral lesions (non-lymph node soft tissue or organ) will be assessed by change in size. PET positive visceral lesions will be considered:
 - a. True positive:
 - If on follow-up imaging within 3-12 months, visceral lesions seen on CT or MRI scan decrease by 30% (for patients undergoing systemic treatment of focal therapy at this site) or increase by 20% in largest diameter.

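### Size-based validation is uneven across lesion classes: the 3 mm minimum covers nodes only, and the prostate true-positive bullet lacks the 3-month start that its false-positive bullet has

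*Combined protocol and SAP*

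**What the plan says.** All the rules are in section 3.5.1, under validation by follow-up imaging.

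- **Lymph nodes, true positive.** At 3-12 months, a short-axis decrease of more than 30% (treated patients) or an increase of more than 20%, "with a minimum of 3 mm in change in size".
- **Visceral lesions, true positive.** "If on follow-up imaging within 3-12 months, visceral lesions seen on CT or MRI scan decrease by 30" (percent, treated patients), "or increase by 20% in largest diameter". No millimetre minimum is given.
- **Prostate and prostate bed, true positive.** "If on follow-up imaging within 12 months, lesions seen on CT or MRI scan decrease by 30" (percent, treated patients), or a 20% increase in largest diameter. There is no millimetre minimum and no 3-month start.
- **Prostate and prostate bed, size-based false positive.** "If on follow-up imaging within 3-12 months, sites of initial" PET-positive lesions shrink by more than 30% without therapy.
- **Default.** In each of these three classes, a lesion that meets neither set of criteria is false positive.
- **PSA bullet.** A PSA fall of more than 50% after targeted treatment gives a true positive, but only if the lesion has not changed in size (less than a 30% decrease or 20% increase).

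On reading, "Interpretation of follow-up imaging will be performed by local read". Section 3.10.1 gives validation to unblinded local investigators who review images and reports, and ranks histopathology above imaging and imaging above PSA. Appendix A places conventional imaging anywhere from Day 8 to one year.

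**The concern.** The plan protects nodes against trivial size changes and gives no reason for omitting that protection elsewhere. The growth criterion carries no treatment condition, so for a small visceral or prostate-bed focus a change of 1 to 2 mm between two reads is enough for a true positive. For prostate lesions the second read may come well before 3 months.

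At stake is the secondary endpoint, PPV by region. Region 1 (prostate bed) is scored without the minimum. Nodes in region 2 (pelvis) are scored with it. Region 3 pools extra-pelvic nodes, scored with it, and visceral lesions, scored without it. A difference between regional PPVs could therefore partly reflect the scoring rule rather than the tracer.

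**Working it through.** **Inputs from the documents.** The 20% growth and 30% decrease thresholds, the 3 mm minimum for nodes, the false-positive default (all 3.5.1), and 255 expected positive patients (3.10.2).

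**Assumed inputs.** The documents give no measurement error and no lesion sizes. I take independent, normally distributed reading errors with SD s = 0.5 to 2 mm per read, and true diameters d of 6, 8 and 10 mm.

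**Step 1: the plan's own precision.** With 0.85 × 300 = 255 positives and an observed PPV of 80% (204/255), the exact 95% interval is 74.6% to 84.7%. This matches the tabulated 75% to 85%. Its half-width is about 5.1 points.

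**Step 2: where a 3 mm minimum bites.** 3/0.20 = 15 mm and 3/0.30 = 10 mm. The minimum raises the hurdle for growth below a measured baseline of 15 mm, and for shrinkage below 10 mm. The growth criterion alone requires 1.2 mm at 6 mm and 2.0 mm at 10 mm.

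**Step 3: unchanged lesion, chance of apparent growth per scan.** Let a be the measured baseline and b the measured follow-up, both with mean d.

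- Without the minimum: P(b ≥ 1.2a) = Φ(−0.2d / (s√(1 + 1.2²))) = Φ(−0.2d / (1.562s)).
- With the minimum, at these sizes: P(b − a ≥ 3) = Φ(−3 / (s√2)).

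| s (mm) | 6 mm | 8 mm | 10 mm | with 3 mm minimum |
|---|---|---|---|---|
| 0.5 | 6.2% | 2.0% | 0.5% | 0.0% |
| 1.0 | 22.1% | 15.3% | 10.0% | 1.7% |
| 1.5 | 30.4% | 24.7% | 19.7% | 7.9% |
| 2.0 | 35.0% | 30.4% | 26.1% | 14.4% |

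At 15 mm and s = 1 mm the figures are 2.7% without and 1.7% with the minimum, so the issue is confined to small lesions.

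**Step 4: the opposite error.** Take a 10 mm lesion that truly grows 25%, to 12.5 mm, with s = 1 mm.

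- It misses the 20% rule with probability Φ(−(12.5 − 12)/1.562) = Φ(−0.32) = 37%.
- With a 3 mm minimum it is missed with probability Φ((3 − 2.5)/1.414) = Φ(0.354) = 64%.

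A missed lesion defaults to false positive unless histology, a later scan or PSA settles it.

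**Step 5: per-patient size, illustrative.** Suppose k of the 255 positive patients have no cancer and rest only on such a lesion, and a share q is scored true positive by error. The shift is 100kq/255 points. It is 0.04 points for k = 5 and q = 2%, and 2.0 points for k = 20 and q = 25%, against the half-width of about 5 points.

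**Step 6: interaction with the PSA bullet.** Suppose a millimetre minimum were applied to every size criterion. A treated 6 mm prostate-bed lesion that shrinks to 4 mm (33%, 2 mm) with a PSA fall above 50% would fail the minimum. It would also be barred from the PSA bullet because its size changed, and would become false positive. Today it is a true positive. A growth-only minimum leaves the same gap for a lesion that measures 20% larger but under 3 mm larger.

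**The case against.** A reader might infer that the uneven rules bias PPV upward. The documents do not support that. The one-way argument covers only lesions whose true size is unchanged. Step 4 shows that error also turns real growth into false positives, and the background section reports correct localization of about 85-87% in a similar population, so many positives may be real disease. An unchanged lesion may also be cancer, in which case a true positive reached by error is still the right label.

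A reader might also infer that any 30% or 20% change suffices. The 30% decrease counts only in treated patients; without therapy a decrease of more than 30% is false positive. Only the 20% increase is unconditional.

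Nor does the missing 3-month start itself add reader noise. It is an asymmetry of window, and the bone follow-up criteria also say only within 12 months.

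Other safeguards count. Histology ranks first and is sought where feasible, follow-up should use the same modality as the initial work-up, and the validators see images as well as reports. These reduce the number of lesions settled by size and the variation between scans. They do not require both diameters to be measured together, and they do not explain the difference between classes.

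Finally, copying the 3 mm minimum everywhere would do harm (steps 4 and 6). That objection stands and limits the fix.

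**Conclusion.** The inconsistency stands on the text. The 3 mm minimum appears only in the node rule, and the prostate true-positive and size-based false-positive bullets use different windows. For an unchanged lesion of 6 to 10 mm settled by imaging, the growth criterion without a minimum yields a true positive by error in about 10% to 22% of scans at an assumed SD of 1 mm, and in 0.5% to 35% across SDs of 0.5 to 2 mm. With the minimum, the corresponding figures are 1.7% and 0% to 14%.

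These figures rest wholly on the assumed error and sizes. The net direction of bias in PPV is not established. The effect on per-patient PPV is probably small, up to about 2 points in the illustration. The case for acting rests on comparability of the regional PPVs and on how little the main changes cost. The 3 mm minimum taken alone is closer to a trade-off than a clear gain.

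**What to change.** 1. Change the imaging bullet for prostate and prostate-bed true positives to 3-12 months, to match its size-based false-positive bullet and the node and visceral rules.
2. Have the validating investigator, who already reviews the images, measure baseline and follow-up diameters side by side at one sitting.
3. Reconcile the 3 mm minimum across classes for the 20% growth criterion only, or report regional PPV with and without it. In either case, reword the PSA bullet so that it applies whenever the size criterion is not met; a lesion below the minimum with a PSA response is then not forced to false positive.

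Do not add growth or the 3 mm minimum to the false-positive bullets.

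Cost: a few bullets of wording and one measuring convention, with no new scan or reader. The downside is that scans before 3 months (for prostate lesions) and, if the minimum is adopted, real growth under 3 mm would no longer confirm a lesion by size. Without a later scan, histology or a PSA response, such lesions count as false positive, which lowers PPV slightly.
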